### 5.2. Study Size

The study is designed to mainly evaluate feasibility and acceptability of some implementation strategies from the feedbacks of SSPs and PSPs using implementation science measures. The study size for SSPs and PSPs will be investigated on the basis of analysis of the standardized effect size

$$d = \frac{\mu(\text{DI}) - \mu(\text{RI})}{\sigma}$$

which is defined as the ratio of difference of mean FIM scores between two arms to the standard deviation  $\sigma$ . To accommodate various scenarios of the mean difference between

arms and the assumed standard deviation, the standardized effect size  $d$  is considered without taking into account the effect of ICC (Intra-Cluster Correlation).

[figure not shown]

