## 4. Implementation Research Methods

### 4.1. Study Arms Overview

The two study arms are routine implementation and dynamic implementation. Clinics will be randomized to the two study arms in a 2:1 distribution, whereby about 12 clinics will be in the dynamic implementation arm and about 6 clinics will be in the routine implementation arm (Note: Number of clinics may vary depending on recruitment). Clinics receiving routine implementation will receive standard provider and patient toolkits that will be available when CAB PrEP is commercially available. Clinics receiving dynamic implementation will receive enhanced toolkits, a digital health end to end implementation strategy, and implementation facilitation. An overview of the RI and DI implementation strategies are outlined in [Table 1](#) and [Table 2](#) in terms of six dimensions as recommended by Proctor and colleagues [[Proctor](#), 2013]: actor, the action, action targets, dose, implementation outcomes addressed, and theoretical justification.

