### Sample Size of SSPs:

For SSPs, its size consideration consists of two parts: one is based on practical considerations in terms of feasibility of enrolling an adequate number of sites on each implementation strategy with the desire to have interventions tested across two types of study sites (high vs low), and the other is to enroll an adequate number of SSPs in each site to achieve the targeted power to detect the various differences between two arms (DI vs RI) in term of their mean FIM score with the cap 90 on the number of SSPs to be enrolled.

With the cap 90 on the number of SSPs and the allocation of SSPs between DI arm and RI arm being 2:1, the absolute value of  $d$  will range approximately from 0.63 to 0.73 if the study power changes from 0.80 to 0.90, as shown in [Table 4](#) below, where [Figure 4](#) illustrates the relationship between  $d>0$  and the study power.

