**Figure 4 Relationship between Standardized Effect Size and Study Power for SSPs**

Results from study CUSTOMIZE (209493) have shown that the estimated mean score of FIM for SSPs was 4.46 with standard deviation (SD) 0.59 at Month 12. Assuming these results remain valid in our RI arm (N1=30) at Month 13 when 90 SSPs are enrolled in DI and RI with ratio 2:1, to achieve 80% power, the mean score  $\mu(\text{DI})$  of FIM at Month 13 for DI arm should be at least 4.83 if DI arm behaves better than RI arm, or at most 4.09 if vice versa, as the absolute mean difference  $|\mu(\text{DI}) - \mu(\text{RI})|$  will be  $0.37 \approx 0.59 * 0.63$  ( $=\sigma^*d$ ). The mean FIM score of DI arm at Month 13 will be at most 4.06 if  $\mu(\text{DI}) < \mu(\text{RI})$  or at least 4.86 if  $\mu(\text{DI}) > \mu(\text{RI})$  to have 85% power. The other scenarios of  $\mu(\text{DI})$  are summarized for the range of detectable standardized effect size and the corresponding powers in [Table 5](#).

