**Table 6 Sensitivity of Sample Size to Standardized Effect Size for SSPs**

d	Target Power	Actual Power	N1 for RI	N2 for DI	Total N
0.6	0.8	0.81	34	68	102
0.6	0.85	0.86	39	78	117
0.6	0.9	0.9	45	90	135
0.63	0.8	0.81	31	62	93
0.63	0.85	0.85	35	70	105
0.63	0.9	0.9	41	82	123
0.66	0.8	0.8	28	56	84
0.66	0.85	0.85	32	64	96
0.66	0.9	0.9	37	74	111
0.69	0.8	0.81	26	52	78
0.69	0.85	0.85	29	58	87
0.69	0.9	0.9	34	68	102
0.72	0.8	0.81	24	48	72
0.72	0.85	0.85	27	54	81
0.72	0.9	0.91	32	64	96
0.75	0.8	0.81	22	44	66
0.75	0.85	0.86	25	50	75
0.75	0.9	0.9	29	58	87

**Figure 5 Relationship between Minimum Sample Size Required for RI Arm and the Assumed Standardized Effect Size for SSPs****Sample Size of PSPs:**

For PSPs, its sample size will be considered in a similar way to that of SSPs. With the cap 220 on the number of enrolled PSPs and the assumption on the dropout rate about 15% across arms, a series of targeted power will be investigated to determine the number of PSPs needed in each arm that will ensure the detection of the various differences between two arms (DI vs RI) in term of mean FIM score of PSPs at Month 13.

[figure not shown]
With the dropout rate 15%, at most 187 out of the capped 220 PSPs will remain in both DI arm and RI arm with the ratio 2:1 at Month 13, and the absolute value of standardized effect size d will range from 0.44 to 0.51 when the study power increases from 0.80 to 0.90 as shown in [Table 7](#), where [Figure 6](#) illustrates the relationship between d>0 and the study power.

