**Figure 6 Relationship between Standardized Effect Size and Study Power for PSPs**

Interim Results from study CARISEL (213199) have shown that the estimated mean score of FIM for PSPs in standard arm was 4.7 with standard deviation (SD) 0.49 at Month 4. Assuming these results remain valid in our RI arm at Month 13 when a total of 220 PSPs are enrolled in DI and RI with ratio 2:1, to achieve 80% power, the mean score of FIM at Month 13 for DI arm should be at least 4.92 if DI arm behaves better than RI arm, or at most 4.48 if vice versa, as the absolute mean difference  $|\mu(\text{DI}) - \mu(\text{RI})|$  will be  $0.22 \approx 0.49 * 0.44$ . The mean FIM score of DI arm at Month 13 will be at most 4.47 if  $\mu(\text{DI}) < \mu(\text{RI})$  or at least 4.93 if  $\mu(\text{DI}) > \mu(\text{RI})$  to have 85% power. The other scenarios of  $\mu(\text{DI})$  are summarized for the range of detectable standardized effect size and the corresponding powers in [Table 8](#).

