**Figure 7 Relationship between Minimum Sample Size Required for RI Arm and the Assumed Standardized Effect Size for PSPs**

### 5.3. Essential Analysis

The primary endpoint in terms of feasibility is SSPs' mean FIM score at Month 13 under Dynamic Implementation (DI) arm and Routine Implementation (RI) arm respectively, and the difference of their mean FIM scores between arms. For FIM of SSPs and the difference between arms, descriptive statistics including 95% confidence intervals will be displayed for these estimates. Mean FIM scores will be compared between the two implementation arms to test if the observed difference is statistically significant. In

addition, distribution of FIM items scores will also be compared. P-values will be reported for these comparisons.

To address the potential intra-cluster correlation effect due to the cluster randomization design, classical methods such as mixed effects linear regression model or Generalized Estimating Equations will be utilized. Besides the analysis on the subject level, the stratification analysis will be performed at the site level to evaluate the impact of the capacity of sites (high volume vs low volume) in responses to two implementation strategies imposed on SSPs. Exploratory analysis will be undertaken to assess the variability of responses by other factors such as subset of implementation strategies.

In addition to summary of mean FIM scores of SSPs at different timepoints, the change in mean FIM scores from baseline will be analyzed at the designated timepoints. For the specific Telehealth implementation strategy on SSPs, the subgroup analysis on FIM scores including change from baseline will be conducted.

The FIM scores of PSPs will be summarized in the same way as those of SSPs. In addition, subgroup analysis on PSPs will include, but not limited to, factors such as demographic, baseline characteristics, study arm, clinic characteristics and APRETUDE initiation method. To address the potential differential dropout rates of PSPs between arms, appropriate imputation methods will be undertaken to handle missing data of different type.

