## **5.7. Limitations of the Research Methods**

The two arms are randomized with ration 2:1 on the site level, which leads to the unbalance of subjects under different interventions. This might reduce the study power with a fixed sample size.

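### The 80–90% power in Section 5.2 treats staff and patients as independent; with about 18 randomised sites it holds only if the intra-cluster correlation is essentially 0

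*Protocol*

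**What the plan says.** The Abstract and Section 4.1 make the site the unit of randomisation: "about 12 clinics will be in the dynamic implementation arm and about 6 clinics will be in the routine implementation arm". Section 3.2 expects about 5 staff study participants (SSPs) per site, varying by site.

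Section 5.2 sizes the trial on d, the difference in mean Feasibility of Intervention Measure (FIM) score divided by its standard deviation. It says that d "is considered without taking into account the effect of ICC (Intra-Cluster Correlation". No ICC value, range or design effect follows. For 90 SSPs (30 routine, 60 dynamic), the detectable |d| "will range approximately from 0.63 to 0.73 if the study power changes from 0.80 to 0.90". For patient study participants (PSPs), with 187 of 220 retained, "the absolute value of standardized effect size d will range from 0.44 to 0.51 when the study power increases from 0.80 to 0.90".

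The section then turns these into results for this trial. "when 90 SSPs are enrolled in DI and RI with ratio 2:1, to achieve 80% power", the dynamic-arm SSP mean must be at least 4.83, a difference of 0.37. For PSPs, "when a total of 220 PSPs are enrolled in DI and RI with ratio 2:1, to achieve 80% power", it must be at least 4.92, a difference of 0.22.

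Section 5.3 plans a mixed model or GEE: "To address the potential intra-cluster correlation effect due to the cluster randomization design". Section 5.7, the limitations section, discusses only the 2:1 site allocation and says of it: "This might reduce the study power with a fixed sample size".

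**The concern.** When sites are randomised and people within a site answer alike, each additional person from the same site adds less information. A power figure for independent individuals then overstates what the trial can show. Section 5.3 accepts that such correlation may exist, but Section 5.2 sizes the trial as if it did not. The mixed model or GEE corrects the standard error; it does not restore the power.

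At stake is how the result is read. A null primary result would be judged against a sensitivity of 0.37 FIM points that the trial may not have. Nothing in Section 5.2 or 5.7 lets a reader see the size of the gap. At a given ICC it is wider for PSPs because there are more of them per site.

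**Working it through.** **Inputs from the protocol.** Sites: 12 and 6, total 18 (Section 4.1). SSPs: 30 and 60 (Table 4), so m = 90/18 = 5 per site. PSPs: 62 and 125 (Table 7), so m = 187/18 = 10.39 per site. FIM standard deviations: 0.59 (SSP) and 0.49 (PSP), Section 5.2. The hypotheses in Section 5.1 are two-sided.

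**Assumptions.** Two-sided alpha of 5%, which the sample-size section does not state but which reproduces its tables. Equal site sizes. ICC of 0.01, 0.05 and 0.10, chosen for illustration because the protocol gives none.

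**Step 1: reproduce the plan.** Two-sample t-test on independent individuals (noncentral t, N − 2 degrees of freedom):

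- SSP 30/60: power 0.796 at d = 0.63 and 0.898 at d = 0.73.
- PSP 62/125: power 0.805 at d = 0.44 and 0.904 at d = 0.51.

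These match Tables 4 and 7. All the routine-arm sizes in Table 6 also reproduce exactly, as do the Table 9 rows checked (d = 0.44, 0.45, 0.47 and 0.51).

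**Step 2: add clustering.** Design effect DE = 1 + (m − 1) × ICC. Noncentrality λ = d × √[n1·n2 / ((n1 + n2) × DE)], where n1·n2/(n1 + n2) is 30 × 60/90 = 20 for SSPs and 62 × 125/187 = 41.44 for PSPs.

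| ICC | SSP DE | SSP effective N (of 90) | PSP DE | PSP effective N (of 187) |
|---|---|---|---|---|
| 0.01 | 1.04 | 86.5 | 1.09 | 171 |
| 0.05 | 1.20 | 75 | 1.47 | 127 |
| 0.10 | 1.40 | 64.3 | 1.94 | 96 |

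Worked examples at ICC 0.05, normal reference. SSP: λ = 0.63 × √(20/1.20) = 2.572, power = Φ(2.572 − 1.960) = 0.730. PSP: λ = 0.44 × √(41.44/1.469) = 2.337, power = Φ(2.337 − 1.960) = 0.647.

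**Step 3: results.** The normal reference isolates the ICC effect. The t reference on 15 degrees of freedom (18 sites less intercept, arm and volume) also counts the small number of sites.

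| Quantity | Stated | Normal, ICC 0.01 / 0.05 / 0.10 | t(15), ICC 0.01 / 0.05 / 0.10 |
|---|---|---|---|
| SSP power, d = 0.63 | 80% | 79 / 73 / 66% | 73 / 67 / 60% |
| SSP power, d = 0.73 | 90% | 89 / 85 / 79% | 85 / 80 / 73% |
| PSP power, d = 0.44 | 80% | 77 / 65 / 53% | 72 / 59 / 48% |
| PSP power, d = 0.51 | 90% | 88 / 77 / 66% | 84 / 72 / 60% |
| SSP FIM difference at 80% power | 0.37 | 0.38 / 0.40 / 0.44 | 0.40 / 0.43 / 0.47 |
| PSP FIM difference at 80% power | 0.22 | 0.22 / 0.26 / 0.30 | 0.24 / 0.28 / 0.32 |

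At ICC = 0 the normal reference returns 80% (SSP) and 81% (PSP) at the lower d; t(15) returns 75% for both.

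**Step 4: break-even.** With the normal reference, SSP power at d = 0.63 drops below 80% at an ICC of about 0.003 and below 75% at about 0.036. For PSPs at d = 0.44 the values are about 0.002 and 0.017. The 80% thresholds are sensitive to the two-decimal rounding of d. A steadier mark is 78% power on the protocol's own t-test with the design effect added; this is reached at an ICC of about 0.010 (SSP) and 0.007 (PSP).

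**Step 5: simulation.** Regression of site means on arm and volume, 18 sites, 40,000 runs, ICC 0.01 / 0.05 / 0.10. Power was 0.737 / 0.671 / 0.603 for SSPs at d = 0.63 and 0.718 / 0.590 / 0.482 for PSPs at d = 0.44, in agreement with the t(15) figures.

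**The case against.** The strongest reply is that the omission is disclosed before any table and that the tables are correct for the condition stated. Both points are true: nothing in Tables 4 and 7 is miscalculated. But the disclosure is a single clause. The text on the dynamic-arm means of 4.83 and 4.92 then claims 80% power for this trial's own enrolment without repeating it, and Section 5.7 leaves clustering out. A reader told that ICC was ignored still cannot tell what that costs.

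Second, the loss for the primary endpoint is modest if ICC is small. This stands. At ICC 0.01 the design effect alone takes SSP power from 80% to 79%, and at 0.05 the detectable d of 0.686 still lies within the protocol's 0.63–0.73. The largest losses are for PSPs, the secondary hypothesis, and staff and patient ICCs need not be equal.

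Third, the t(15) reference is a choice. Section 5.3 fixes no degrees of freedom, and the fall to 75% at ICC = 0 reflects the few sites, not the ICC. That is why both references are shown. Using 16 degrees of freedom changes these powers by less than one percentage point.

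Fourth, adjusting for clinic volume could lower the residual ICC. No gain is counted because the protocol gives no figure. Unequal site sizes, also not counted, would lower power further.

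Finally, Section 5.1 names a two-way ANOVA with clinic volume and no site term, which might seem to keep the stated power. It would not hold the 5% level. Simulated with 5 and 10 people per site (4,000 runs), it had a type I error of about 7% and 10% for SSPs and 11% and 16% for PSPs at ICC 0.05 and 0.10.

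**Conclusion.** The concern holds. The stated 80–90% power is individually randomised power attached to a trial that randomises about 18 sites. A valid 5% test reaches it only if ICC is essentially 0, and with a site-level t reference it falls somewhat short even then. Across the assumed ICCs of 0.01–0.10, power at the effects tied to 80% is 60–79% for the primary SSP comparison and 48–77% for PSPs, taking both references together. These ranges rest on the assumed ICCs, equal site sizes and no gain from volume adjustment. The fault lies in the stated power and detectable differences; it gives no reason to change the number of sites or participants.

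**What to change.** Keep the caps of 90 SSPs and 220 PSPs, and in Section 5.2:

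- Restate Tables 4, 5, 7 and 8, and the text built on them, as detectable d and detectable FIM difference at 80, 85 and 90% power. Use DE = 1 + (m − 1) × ICC over a stated range, for example 0.01–0.10, with a cluster-level t reference.
- Label Tables 6 and 9 as ICC = 0 (individually randomised) figures. Give the same label to the worked examples drawn from them (84 and 96 SSPs; 209 and 240 PSPs) and to Figures 5 and 7; bring Figures 4 and 6 into line with the restated tables.
- Say which test the power refers to, so that the ANOVA in Section 5.1 and the clustered model in Section 5.3 agree.

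In Section 5.7, add one sentence naming clustering within about 18 sites as a limit on power.

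The cost is recalculated tables and edited text. No sites, participants or procedures are added. The only downside is a less favourable stated power.

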### Sample Size of SSPs:

For SSPs, its size consideration consists of two parts: one is based on practical considerations in terms of feasibility of enrolling an adequate number of sites on each implementation strategy with the desire to have interventions tested across two types of study sites (high vs low), and the other is to enroll an adequate number of SSPs in each site to achieve the targeted power to detect the various differences between two arms (DI vs RI) in term of their mean FIM score with the cap 90 on the number of SSPs to be enrolled.

With the cap 90 on the number of SSPs and the allocation of SSPs between DI arm and RI arm being 2:1, the absolute value of  $d$  will range approximately from 0.63 to 0.73 if the study power changes from 0.80 to 0.90, as shown in [Table 4](#) below, where [Figure 4](#) illustrates the relationship between  $d>0$  and the study power.

**Table 4      Sensitivity of the Absolute Value of Standardized Effect Size to Study Power for SSPs**

Power	N1	N2	N	Absolute Value of $d$
0.8	30	60	90	0.63
0.81	30	60	90	0.64
0.82	30	60	90	0.65
0.83	30	60	90	0.66
0.84	30	60	90	0.67
0.85	30	60	90	0.68
0.86	30	60	90	0.69
0.87	30	60	90	0.7
0.88	30	60	90	0.71
0.89	30	60	90	0.72
0.9	30	60	90	0.73

**Figure 4 Relationship between Standardized Effect Size and Study Power for SSPs**

Results from study CUSTOMIZE (209493) have shown that the estimated mean score of FIM for SSPs was 4.46 with standard deviation (SD) 0.59 at Month 12. Assuming these results remain valid in our RI arm (N1=30) at Month 13 when 90 SSPs are enrolled in DI and RI with ratio 2:1, to achieve 80% power, the mean score  $\mu(\text{DI})$  of FIM at Month 13 for DI arm should be at least 4.83 if DI arm behaves better than RI arm, or at most 4.09 if vice versa, as the absolute mean difference  $|\mu(\text{DI}) - \mu(\text{RI})|$  will be  $0.37 \approx 0.59 * 0.63$  ( $=\sigma^*d$ ). The mean FIM score of DI arm at Month 13 will be at most 4.06 if  $\mu(\text{DI}) < \mu(\text{RI})$  or at least 4.86 if  $\mu(\text{DI}) > \mu(\text{RI})$  to have 85% power. The other scenarios of  $\mu(\text{DI})$  are summarized for the range of detectable standardized effect size and the corresponding powers in [Table 5](#).

**Table 5 The Mean FIM Score of DI Arm at Month 13 Assuming  $\mu(\text{RI})=4.46$  and  $\text{SD}=0.59$  for SSPs**

[figure not shown]
Absolute Value of d	Power	$\mu(\text{DI})$ if $\mu(\text{DI}) < \mu(\text{RI})$	$\mu(\text{DI})$ if $\mu(\text{DI}) > \mu(\text{RI})$
0.63	0.8	4.09	4.83
0.64	0.81	4.08	4.84
0.65	0.82	4.08	4.84
0.66	0.83	4.07	4.85
0.67	0.84	4.06	4.86
0.68	0.85	4.06	4.86
0.69	0.86	4.05	4.87
0.7	0.87	4.05	4.87

Absolute Value of d	Power	$\mu(DI)$ if $\mu(DI) < \mu(RI)$	$\mu(DI)$ if $\mu(DI) > \mu(RI)$
0.71	0.88	4.04	4.88
0.72	0.89	4.04	4.88
0.73	0.9	4.03	4.89

If we consider a series of standardized effect size d, [Figure 5](#) below summarizes the corresponding minimum sample size N1 of RI arm needed to achieve three target powers (80%, 85%, 90%). For the exact sample size of SSPs and their allocation to each arm for d ranging from 0.6 to 0.75, please refer to [Table 6](#). For instance, if we expect the standardized effect size to be 0.66 which is a little larger than 0.63 discussed above, then a total of 84 SSPs is required with 28 in RI arm and 56 in DI arm to achieve 80% power. And approximately 96 SSPs are needed to have 85% power, where 32 SSPs are allocated to RI arm and 64 to DI arm.

**Table 6 Sensitivity of Sample Size to Standardized Effect Size for SSPs**

d	Target Power	Actual Power	N1 for RI	N2 for DI	Total N
0.6	0.8	0.81	34	68	102
0.6	0.85	0.86	39	78	117
0.6	0.9	0.9	45	90	135
0.63	0.8	0.81	31	62	93
0.63	0.85	0.85	35	70	105
0.63	0.9	0.9	41	82	123
0.66	0.8	0.8	28	56	84
0.66	0.85	0.85	32	64	96
0.66	0.9	0.9	37	74	111
0.69	0.8	0.81	26	52	78
0.69	0.85	0.85	29	58	87
0.69	0.9	0.9	34	68	102
0.72	0.8	0.81	24	48	72
0.72	0.85	0.85	27	54	81
0.72	0.9	0.91	32	64	96
0.75	0.8	0.81	22	44	66
0.75	0.85	0.86	25	50	75
0.75	0.9	0.9	29	58	87

**Figure 5 Relationship between Minimum Sample Size Required for RI Arm and the Assumed Standardized Effect Size for SSPs****Sample Size of PSPs:**

For PSPs, its sample size will be considered in a similar way to that of SSPs. With the cap 220 on the number of enrolled PSPs and the assumption on the dropout rate about 15% across arms, a series of targeted power will be investigated to determine the number of PSPs needed in each arm that will ensure the detection of the various differences between two arms (DI vs RI) in term of mean FIM score of PSPs at Month 13.

[figure not shown]
With the dropout rate 15%, at most 187 out of the capped 220 PSPs will remain in both DI arm and RI arm with the ratio 2:1 at Month 13, and the absolute value of standardized effect size d will range from 0.44 to 0.51 when the study power increases from 0.80 to 0.90 as shown in [Table 7](#), where [Figure 6](#) illustrates the relationship between d>0 and the study power.

**Table 7 Sensitivity of the Absolute Value of Standardized Effect Size to Study Power for PSPs**

Power	N1	N2	N	Absolute Value of d
0.8	62	125	187	0.44
0.81	62	125	187	0.44
0.82	62	125	187	0.45
0.83	62	125	187	0.46
0.84	62	125	187	0.46
0.85	62	125	187	0.47
0.86	62	125	187	0.47

Power	N1	N2	N	Absolute Value of d
0.87	62	125	187	0.48
0.88	62	125	187	0.49
0.89	62	125	187	0.5
0.9	62	125	187	0.51

**Figure 6 Relationship between Standardized Effect Size and Study Power for PSPs**

Interim Results from study CARISEL (213199) have shown that the estimated mean score of FIM for PSPs in standard arm was 4.7 with standard deviation (SD) 0.49 at Month 4. Assuming these results remain valid in our RI arm at Month 13 when a total of 220 PSPs are enrolled in DI and RI with ratio 2:1, to achieve 80% power, the mean score of FIM at Month 13 for DI arm should be at least 4.92 if DI arm behaves better than RI arm, or at most 4.48 if vice versa, as the absolute mean difference  $|\mu(\text{DI}) - \mu(\text{RI})|$  will be  $0.22 \approx 0.49 * 0.44$ . The mean FIM score of DI arm at Month 13 will be at most 4.47 if  $\mu(\text{DI}) < \mu(\text{RI})$  or at least 4.93 if  $\mu(\text{DI}) > \mu(\text{RI})$  to have 85% power. The other scenarios of  $\mu(\text{DI})$  are summarized for the range of detectable standardized effect size and the corresponding powers in [Table 8](#).

**Table 8 The Mean FIM Score of DI Arm at Month 13 Assuming  $\mu(\text{RI})=4.7$  and  $\text{SD}=0.49$  for PSPs**

Absolute Value of d	Power	$\mu(\text{DI})$ if $\mu(\text{DI}) < \mu(\text{RI})$	$\mu(\text{DI})$ if $\mu(\text{DI}) > \mu(\text{RI})$
0.44	0.8	4.48	4.92
0.44	0.81	4.48	4.92
0.45	0.82	4.48	4.92
0.46	0.83	4.47	4.93
0.46	0.84	4.47	4.93
0.47	0.85	4.47	4.93
0.47	0.86	4.47	4.93
0.48	0.87	4.46	4.94
0.49	0.88	4.46	4.94
0.5	0.89	4.46	4.95
0.51	0.9	4.45	4.95

If we consider a series of standardized effect size d, [Figure 7](#) below summarizes the corresponding minimum sample size N1 of RI arm needed to achieve three target powers (80%, 85%, 90%). For the exact sample size of PSPs and their allocation to each arm for d ranging from 0.44 to 0.51, please refer to [Table 9](#) below, where N1' is the Dropout-Inflated enrollment sample size for RI arm, N2' is the Dropout-Inflated enrollment sample size for DI arm and N' is the total enrollment sample size for PSPs with dropout rate 15% across arms.

[figure not shown]
For instance, if we expect the standardized effect size to be 0.45 which is slightly higher than 0.44 discussed above, then a total of 209 PSPs is required to be enrolled with 70 in RI arm and 139 in DI arm to achieve 80% power, while 59 PSPs and 118 PSPs are remained in each arm respectively at Month 13. And approximately 240 PSPs are needed in the enrollment to have 85% power, where 80 PSPs are allocated to RI arm and 160 to DI arm, and 68 PSPs and 136 PSPs are retained in each arm respectively at Month 13.

